### **2.1.2 Secondary objectives**

- To assess the diagnostic efficacy of mangoral in liver MRI in terms of:
  - number of lesions detected by each MRI method (unenhanced MRI, mangoral-enhanced MRI, and CMRI)
  - visualisation of detected focal liver lesions in mangoral-enhanced MRI compared to unenhanced MRI (determination of visualisation will be done in the same way as for the primary efficacy variable)
  - confidence in lesion detection and localisation separately in unenhanced MRI, mangoral-enhanced MRI, and CMRI
  - lesion dimensions (independent off-site readers' assessment): longest diameter of the largest and the smallest lesion
  - quantitative assessments by measuring percent signal intensity enhancement of liver, liver-to-lesion contrast, signal-to-noise ratio, and contrast-to-noise ratio of up to 5 lesions per patient
  - number of patients who had at least one new lesion identified on CMRI compared to unenhanced MRI alone
- To assess a proportion of patients having at least one malignant lesion identified on post-mangoral images that was not identified on pre-mangoral images.
- To evaluate the safety and tolerability of mangoral
- To evaluate the pharmacokinetics of manganese after a single dose of mangoral in a subgroup of patients (including a small number of dialysis patients)
- To evaluate the impact of diagnostic performance of CMRI and mangoral-enhanced MRI versus unenhanced MRI on the patients' management.

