Follow-up evaluations (FU 1, FU 2, FU 3) will be performed on 3 visits following contrast administration, at 24 ( $\pm$  4) hours, 48 ( $\pm$  4) hours, and 5 ( $\pm$  2) days post-dose, for safety assessments including clinical safety laboratory tests, measurement of blood manganese, ECG, vital signs, physical examination, including neurological assessments. Changes in concomitant therapies will be recorded. Follow-up evaluations at 24 ( $\pm$  4) hours and 48 ( $\pm$  4) hours can at the discretion of the investigator be performed as remote visits when required to ease the burden for the patient. Participants in the PK subgroup are required to have all assessments including blood samples as scheduled.

An additional follow-up visit (FU 4) for the optional brain MRI may be performed 7 (+ 2) days after mangoral-enhanced MRI of the liver only in those patients who underwent brain MRI due to any clinical reason within the last 6 months prior to mangoral-enhanced MRI and for whom previous brain MRI images are available for comparison (Section 6.2.4.1.2).

In a subgroup of patients, additional blood samples (6 mL per time point) will be drawn for the determination of pharmacokinetic parameters on the day of the liver MRI examination (day 0) at 0.25, 0.5, 1, 2, 3, 4, 6, 8, and 12 hours post-dose (Section 6.4). This PK subgroup will consist of 12 patients, including 4 patients currently on maintenance haemodialysis.

Each unenhanced and each mangoral-enhanced liver MRI examination will consist of axial T1- and T2-weighted image sequences and a diffusion-weighted imaging (DWI) sequence. Details of MRI acquisition parameters are described in Section [6.2.4.1.1](#).

Primary diagnostic efficacy in terms of visualisation of detected focal liver lesions will be evaluated centrally at an imaging core laboratory by 3 independent readers (Section [6.2.5](#)). Reading will be performed in 3 parts (Part I: unenhanced MRI alone; Part II: combined MRI, i.e. paired reading of both unenhanced and mangoral-enhanced images; Part III: mangoral-enhanced MRI alone). There will be a minimum 2-weeks gap between the reads to reduce recall bias. All independent central readers will be blinded to clinical data, site, and country information.

The site investigators will also evaluate unenhanced and mangoral-enhanced MRI images (on-site read). Their assessments will be used for the analysis of secondary variables.

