### 3.1 Discussion of study design

Mangoral is currently being developed for visualisation of focal liver lesions, including liver metastases, in patients where the use of GBCAs may be medically inadvisable or cannot be administered. Patients with severe renal impairment are at risk of experiencing serious adverse effects if they are given any of the intravenously administered contrast agents currently available on the market for liver MRI enhancement. NSF is a rare, but potentially fatal, complication of GBCAs that has been reported in patients with renal failure [\[21\]](#).

Previous clinical Phase I and II studies included healthy volunteers and patients with liver metastases. This Phase III study will be performed to assess the safety and diagnostic efficacy of mangoral in a patient cohort with severe renal impairment (eGFR < 30 mL/min/1.73 m^2, or increase in serum creatinine  $\geq$  0.3 mg/dL within 48 hours or  $\geq$  50% within 7 days) and who are being evaluated for known or suspected focal liver lesions. In addition, as patients with severe renal impairment are likely to need dialysis, patients on haemodialysis or peritoneal dialysis will be included in this study to obtain information on safety, pharmacokinetics, and diagnostic efficacy of mangoral in such patients.

A multicentre and multinational design is used to increase representativeness and to reduce bias.

Results of a previous clinical Phase II study demonstrated that signal intensity enhancement increased in liver parenchyma until 3 hours post-dose and there was no significant difference in the liver-to-lesion contrast between 3 and 6 hours after mangoral administration [\[16\]](#). Thus, the primary time point for mangoral-enhanced liver MRI chosen in this study is 4 hours after intake with a time window of  $\pm$  1 hour.

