10.3 Analysis Populations

All patients enrolled in the study (fulfil all inclusion criteria, but none of the exclusion criteria and have been included in the clinical study at Visit 2) will be included in the safety analysis (safety population). The efficacy analysis will be performed in the full analysis set of patients (i.e. who have taken a single dose of the investigational medicinal product) and on a 'per protocol' basis, see definitions below ([Table 5](#)).

Table 5 Definition of analysis populations

Population	Description
Screened Patients	All patients with date of informed consent not missing.
Safety population (SAF) and enrolled patients	All patients enrolled in the study (fulfil all inclusion criteria, but none of the exclusion criteria and have been included in the clinical study at Visit 2).
Dosed Patients	All patients of the safety population who received the IMP.
Full analysis set (FAS)	All patients of the safety population who received the IMP and for whom the primary efficacy variable is assessable, i.e. all unenhanced / enhanced liver MRI images are assessable.
Per protocol set (PPS)	The 'per protocol' set defines the subset of the patients in the FAS without important protocol deviations that could affect the study objectives. All important protocol deviations will be manually reviewed by ICON and Ascelia to agree which to exclude from PPS.
PK population (PKS)	Defines the subset of patients in the FAS who have a blood sample taken at a PK timepoint (0.5, 1, 2, 3, 4, 6, 8 or 12 hours post-dose). These patients will be selected from a few sites that are able to include these patients and follow PK requirements.
Dialysis subgroup population (DSP)	All in the FAS currently on maintenance hemodialysis.
Brain MRI subgroup population (BMSP)	All patients in the FAS with brain MRI performed within 6 months prior to V3 who underwent the optional brain MRI 7 (+2) days after mangoral-enhanced MRI of the liver.

Demographic data and baseline characteristics will be displayed for the SAF, FAS and PPS populations. Efficacy data will be displayed for the FAS and the PPS populations. Safety data will be displayed for the SAF population. Manganese blood concentration data will be displayed for the FAS population, but PK parameters data will only be displayed for the PKS population.

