13.7.4 Pharmacokinetic Analysis

The analysis of PK parameters will be performed using the PK Set (PKS). Descriptive and graphical methods will be used to summarize the study results.

The CV and the geometric mean will be additionally included in the descriptive analyses of PK parameters, except for t_{max} . The 2-sided 95% confidence intervals for the geometric means of C_{max} , AUC_{0-t} and AUC will be constructed.

Missing data will be treated as such and will not be imputed or replaced in any way if not specified otherwise.

Individual, mean and overlay blood concentration-time profiles will be plotted on both linear and semi-logarithmic scales. Individual values and descriptive statistics for blood concentration data will be presented by the nominal time point using the Safety Population.

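### The SAP specifies no separate summary of manganese exposure in the four planned haemodialysis patients, and SAP 10.3 and 13.7.4 name different populations for manganese concentrations

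*SAP*

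**What the plan says.** **The PK subgroup.** Protocol section 3 fixes its make-up: "This PK subgroup will consist of 12 patients, including 4 patients currently on maintenance haemodialysis". Protocol 2.1.2 names dialysis patients within the PK objective. Protocol 3.1 gives the reason for enrolling them: "patients on haemodialysis or peritoneal dialysis will be included in this study to obtain information on safety, pharmacokinetics, and diagnostic efficacy" of the product in such patients.

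**PK parameters.** SAP 10.3 limits their display to the PK set (PKS): "Manganese blood concentration data will be displayed for the FAS population, but PK parameters data will only be displayed for the PKS population". SAP 13.7.4 analyses them on the same set and mentions no split by dialysis status. It also calls for individual, mean and overlay concentration profiles.

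**The dialysis population.** SAP Table 5 defines the DSP as: "All in the FAS currently on maintenance hemodialysis". Protocol Table 10 confined it to PK-subgroup members. SAP 7.1 declares that the definition was amended but gives neither a reason nor a use. The only output it receives is the count that SAP 13.1 requires for every analysis population.

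**Manganese concentrations.** SAP 10.3 assigns them to the FAS in the sentence quoted above. SAP 13.7.4 says: "Individual values and descriptive statistics for blood concentration data will be presented by the nominal time point using the Safety Population". SAP 10.3 also says that safety data are displayed on the safety population (SAF). Blood manganese is a safety variable in the protocol synopsis and sits under Safety Parameters in SAP 9.2.4.6.

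**The concern.** A third of the PK subgroup is reserved for haemodialysis patients, and the protocol says it wants PK information in dialysis patients. A plan that pools all 12 into one set of summary statistics gives no estimate for the group that was deliberately included. If exposure differs by dialysis status, the pooled figure describes neither group and hides most of the difference. The set that could carry a separate summary exists in the SAP but is not used for one.

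The population conflict is a separate matter. FAS membership depends on whether the liver images can be assessed, which is not an exposure criterion. If 10.3 were followed, patients would leave the summaries of a safety variable because of image quality.

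**Working it through.** **Step 1: which outputs use the DSP?** I looked for it wherever the SAP assigns populations to outputs.

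| SAP place | Populations named | DSP used? |
|---|---|---|
| 10.3, display rules | SAF, FAS, PPS, PKS | No |
| 13.1, disposition | Count of every population | Count only |
| 13.6, IMP administration | SAF, FAS, PPS, PKS | No |
| 13.7.3, subgroups | FAS, split by field strength, lesion type, age, eGFR, sex | No |
| 13.7.4, PK | PKS; Safety Population for concentrations | No |
| 13.8, safety | SAF | No |

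Protocol 8.1.7 does not fill the gap. It asks for descriptive PK summaries and patient-level plots on the PK population, again without a split.

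**Step 2: what does pooling hide?** The documents give 12 PK patients, 4 of them on maintenance haemodialysis, so 8 others and a share of 4/12 = 33%. The documents give no exposure ratio. R, the geometric mean in haemodialysis patients divided by that in the other 8, is my assumption.

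Pooled geometric mean = (mean of the other 8) × R^(4/12), that is, × R^(1/3). Relative to the haemodialysis mean it is R^(1/3) / R.

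| Assumed R | Pooled ÷ other 8 | Pooled ÷ haemodialysis |
|---|---|---|
| 1 | 1.00 | 1.00 |
| 1.5 | 1.14 | 0.76 |
| 2 | 1.26 | 0.63 |
| 3 | 1.44 | 0.48 |

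A doubling of exposure in the haemodialysis group would raise the pooled value by only 26%.

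**Step 3: how precise would a separate summary be?** The 95% CI for a geometric mean is the estimate divided and multiplied by exp[t(0.975, n−1) × √ln(1+CV²) / √n]. The CVs are assumed.

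| Assumed CV | Factor, n = 4 | Factor, n = 8 |
|---|---|---|
| 30% | 1.60 | 1.28 |
| 50% | 2.12 | 1.48 |
| 80% | 3.06 | 1.80 |

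A summary of 4 patients is descriptive at best, so individual values must accompany it.

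**Step 4: might fewer than 4 remain?** SAP Table 5 makes both the PKS and the DSP subsets of the FAS. A fully sampled patient with a non-assessable MRI therefore drops out of both. At the SAP's 75% evaluable, 4 × 0.75 = 3.0 haemodialysis patients are expected to remain, and all 4 remain with probability 0.75⁴ = 32%. At the 85% assumed earlier in the planning, the figures are 3.4 and 0.85⁴ = 52%. Both probabilities assume independence between patients.

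**Step 5: the concentration population.** Two current sentences of the SAP, in 10.3 and 13.7.4, name different sets and cannot both be followed. The v4.0 entry in the change history records a move of concentration data from the full analysis set to the safety set. The conflict does not depend on that entry, which shows only which way the sponsor meant to go. SAP 9.3 plans for at least 80 patients with both MRI examinations and about 75% evaluable: 80 × 0.25 = 20 patients would be summarised under 13.7.4 but not under 10.3. Using its 59 evaluable patients directly gives 80 − 59 = 21.

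**The case against.** The strongest reply is that nothing is lost. The haemodialysis patients enter every PKS statistic, SAP 13.7.4 plots individual profiles and presents individual concentrations, and SAP 10.1 lists all data. With 4 patients, individual display is a defensible way to show exposure. The PK objective in protocol 2.1.2 asks for pharmacokinetics in a subgroup that includes some dialysis patients, not for separate estimates. This stands against any reading that the exposure data go unreported or that the PK objective fails. It does not dispose of the point: the SAP does not require profiles or listings to be identified by dialysis status, and protocol 3.1 wants information in dialysis patients specifically.

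Second, the documents give no reason to expect a two- or threefold difference. Protocol 1.3 describes a hepatic first-pass effect of about 95% and biliary excretion. That stands: the values of R show how pooling behaves and predict nothing about the size of a difference.

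Third, the TFL shells are a separate document and were not available. A table by dialysis status may already be there. The SAP, however, does not call for one.

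Fourth, the FAS sentence in 10.3 looks like a leftover, since the change history records the intended set. I agree. It remains operative text and needs correcting.

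**Conclusion.** Both parts hold. The SAP specifies no separate summary of exposure in the planned maintenance-haemodialysis patients, and its DSP has no analytical use. SAP 10.3 contradicts 13.7.4, and its own rule for safety data, on the population for manganese concentrations. Neither part touches the primary analysis, the type I error or the sample size.

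The size of the first part is conditional. Pooling shrinks any ratio R to R^(1/3), and R is illustrative. The size of the second is about 20 of 80 patients if 10.3 were followed, resting on the SAP's 75% assumption.

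A reader might infer more than the documents support:

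- **That most DSP members have no PK profile.** The documents do not say how many FAS patients are on haemodialysis. Under the SAP definition a DSP member need not have a profile, and no more can be said.
- **That the other 8 are non-dialysis patients.** Protocol 3.1 also admits peritoneal dialysis, and nothing bars such patients from the PK subgroup.
- **That manganese data would be lost under 10.3.** They would leave the summaries but remain in the listings.

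**What to change.** 1. In SAP 10.3 and 13.7.4, add descriptive summaries of C_max, AUC and t_max, and concentration profiles with individual values, by maintenance-haemodialysis status (yes/no). Use PKS patients who are also in the DSP (planned n = 4) against the remaining PKS patients (planned n = 8), and identify any peritoneal dialysis patient among the latter. Keep the pooled PKS summary. The SAP's DSP definition can stay, because its overlap with the PKS is enough for a PK table.
2. In SAP 10.3, replace the FAS with the Safety Population for manganese concentrations, to agree with 13.7.4 and the change history. Name the set exactly: Table 5 separates the Safety Population (enrolled) from Dosed Patients.

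The cost is SAP wording and a few descriptive outputs from data already collected. The drawback is very imprecise summaries at n = 4, which is why individual values should be shown. The change does not recover a PK patient whose MRI is not assessable, because the PKS stays within the FAS. The report should therefore state how many of the 4 remain. If the TFL shells already contain the split, only the SAP text needs to change.

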10.4 Protocol Deviation

The relevant protocol deviations have to be defined by a systematic data review prior to database closure and unblinding. For this purpose, protocol deviations that occurred during the study such as deviations of inclusion/exclusion criteria or forbidden concomitant medications or patient non-compliance will be assessed as 'important' depending on their potential to interfere with the primary endpoint and the safety endpoints of the study. Listings will be prepared to show the eligibility of all patients. Comprehensive justification for the classification of a protocol deviation as "important" will be given in the integrated clinical study report.

Important protocol deviations and the assessment of analysis sets will be defined during last data review before database closure. All definitions given in the Minutes of the Final Data Review will be taken into account in the analysis.

The list of protocol deviations will be reviewed by the Medical Director, discussed with and approved by sponsor and finalized before locking the database. The sponsor will identify important protocol deviations which will lead to the exclusion of patients from the per protocol set (PPS). Important protocol deviations related to study objectives for patients excluded from PPS will be flagged in the protocol deviation listing.

11.0 Conventions and Derivations

11.1 Data Handling

11.1.1 Imputation of missing data

There will be no imputation of missing data. All data will be analyzed as they appear in the database. Missing data will be displayed in patient data listings and will be declared in tables as appropriate.

11.1.2 Handling of dates and times

- Adverse events with unknown onset date/time will be counted as treatment emergent AEs.
- Adverse events with unknown end date/time will be counted as an ongoing AEs, in addition to those marked as ongoing in the CRF.
- Adverse events with unknown relationship to IMP will be counted as related in AE summary tables.
- Any adverse events with missing seriousness will be counted as serious in AE summary tables.
- Adverse events with partial onset/end date/time will be treated as specified in [Section 15.1.4.1](#).
- For medications with partial end dates see [Section 15.1.3.2](#).

11.1.3 Representation of Missing Data

Times should be printed in the format "HR:MI". "HR" represents the 2-digit hour portion of the time of 24h-format. "MI" represents the 2-digit minute portion of the time. Both hour and minute portions of time are zero padded integer values. Missing time portions should be represented on patient listings as dashes ("10:--" and/or "--:--").

11.2 Definitions and Derived Variables

11.2.1 Definitions

For the statistical analysis, the different MRI methods will be denoted according to the following table.

Table 6 Labeling of MRI methods

MR1 Method	Short label (for tables etc.)
unenhanced MRI	UnMRI
mangoral-enhanced MRI	MeMRI
combined MRI (mangoral-enhanced MRI plus unenhanced MRI)	CMRI

In the following table, the definitions and calculation of derived variables are summarized.

Table 7 Further definitions

Variable / Term	Definition / Way of calculation
Baseline	The last assessment made before the administration of IMP will be used as baseline.

Variable / Term	Definition / Way of calculation
Change from baseline at visit	The difference between a value at time point and the value at baseline
Study day	
The day of IMP is defined as study Day 1.
 
Calculate the study day according to the following rules:
 
If date < date of IMP, then study day = date of IMP - Date.
 
If date ≥ date of IMP, then study day = Date – date of IMP + 1.

Age [years]	Year of informed consent – Year of birth
Age categories	
≥ 18 - < 65 years
 
≥ 65 - < 75 years
 
≥ 75 years

Body Mass Index (BMI)	$\text{BMI [kg/m}^2\text{]} = \frac{\text{Weight [kg]}}{\text{Height [m}^2\text{]}}$
Study duration [days]	Date of completion/discontinuation – date of informed consent + 1
Prior medication	
Any medication taken and stopped before the date of administration of mangoral.
 
If the end date of prior medication is missing or partial see Section 15.1.3.2.

Concomitant medication	
Any medication taken prior to the administration of mangoral and continuing after treatment or started after the date of administration of mangoral.
 
If the end date of concomitant medication is missing or partial see Section 15.1.3.2.

Adverse events	All untoward medical occurrences after signing the informed consent. These can be adverse events either prior to treatment or after treatment as collected in the CRF.
Time to onset of adverse events	Time to onset of adverse events will be calculated based on the administration start date time of IMP based on the imputed value for adverse event start date/time.
Duration of adverse events	
Duration of adverse events will be calculated based on the imputed values for adverse event start date/time and stop date/time.
 
If the duration of the adverse event could not be calculated due to unknown date information, the following assessment to categories will be used:
 
 If the adverse event is marked as "ongoing" in the CRF or the end date is missing, the duration will be categorized as "ongoing". Otherwise, the duration category will be set to "missing".
Flagging of laboratory parameters	Continuous parameters will be classified as low , normal , or high based on reference (normal) ranges. In addition, laboratory parameters are flagged also according to CTCAE grading (G) as G1, G2, G3, or G4
Reproducibility	A consistency of results obtained when the same imaging is performed at short intervals on the same patients using different methods and by different readers.
QTcB interval (msec)	$\text{QTcB interval (msec)} = \frac{\text{QT interval (msec)}}{(\text{RR interval (sec)})^{1/2}}$

Variable / Term	Definition / Way of calculation
QTcF interval (msec)	$\text{QTcF interval (msec)} = \frac{\text{QT interval (msec)}}{(\text{RR interval (sec)})^{1/3}}$

The raw datasets will be in the Study Data Tabulation Model (SDTM) and the analysis datasets will be in the Analysis Data Model (ADaM), where ADaM datasets are derived from SDTM datasets. Throughout the entire study only one CDISC version will be used, there will be no change even if a higher version is available.

